**Figure 3: Hypothesized pathway via which VITAL start may improve partner outcomes and maternal retention and adherence**

**Control Group:** Patients randomized to the control arm will receive the usual standard of care (SOC) pre ARV initiation education with the National ARV Educational Flipchart (typically takes one hour).

**Study Duration:** We estimate enrolling all subjects within 3 years and will follow subjects until the last woman has reached 12 month follow up

**Follow up:** Participants will be asked to attend a study follow-up visit at 1 month, 3 months, 6 months and 12 months after enrollment, at a separate location and time from where they receive their ART refills to reduce confounding. Surveys may be done via phone if that is the participant's preference. At these visits, women will be asked to complete an outcome assessor-administered survey with validated tools to a brief knowledge, motivations and behaviors assessment, experience of intimate partner violence (IPV), partner HTC/sexual history, adherence self-efficacy, perceived social support, perception of received health services support, alcohol and drug use, anxiety and depression screening and ART side effects. Dried blood spots for viral load (VL) testing will be collected at 6- and 12 months. We will collect an additional dry blood spot (DBS) at the 12-month visit. There will be shipped to the University of North Carolina Clinical Pharmacology and Analytical Chemistry Laboratory at Chapel Hill, North Carolina, USA for pharmacokinetic analysis. If participants fail to attend follow-up visits, tracing will be attempted by study staff. Consistent with other studies in Malawi, a transport allowance will be provided for each study visit.

#### **Sample Size Calculation:**

The primary outcome for this study is a composite outcome of retention in care and maternal viral suppression that has been used in similar previous studies. This outcome was selected to measure the ultimate goal of ART use within PMTCT services: to keep HIV+ mothers engaged in care and virally suppressed to maximize the benefits of ART for both treatment and prevention. This outcome assumes that those not retained are not virally suppressed. The sample size calculation is

based on a comparison of the proportions of those in the intervention versus SOC arms reaching the combined primary endpoint at 12 months after maternal ART initiation. Pearson Chi-square test for Proportion Difference was used for calculation. A combination of various scenarios was considered for retention in care (50-90%), maternal viral suppression (50-90%) among those retained, and contamination rate (0-15%). A difference of 15% was selected as the smallest difference that would be of clinical significance. It is also assumed that an effect of this magnitude could be anticipated in this field of research.

For the primary analysis in all subjects, accounting for up to a 15% contamination rate (pilot data suggests 0% contamination) and assuming 1:1 allocation ratio, and 5% attrition (based on transfer out rates from Ministry of Health data at study clinics in 2016) to achieve 90% power to detect a minimum difference of 15% between the control and intervention group, 796 subjects are required (398/398 per arm) at a significance level=0.025 to account for multiple comparisons. Given the anticipated policy change to a dolutegravir-based regimen in the near future, we have further increased the sample size by 12%, to 446 per arm. This increase was done due to published evidence demonstrating higher rates of viral suppression and lower rates of discontinuation in patients on dolutegravir-based regimens. We increased the sample size because this would make a difference between our study and control groups more difficult to measure. We will also plan to have a small pilot of new trial tools and procedures. We estimate that approximately n= 30 to 50, will be needed for adequate piloting. However, given much less contamination than anticipated and disruptions caused by the COVID-19 pandemic which culminated in complete suspension of enrollment from April through July 2020, the study enrolled 800 participants in total.

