## Outcome Measures

The main study outcomes are (1) composite of retention and adherence (viral suppression); (1b) behavioral adherence; and (1c) knowledge and psychosocial impact. Additional outcomes and schedule of measures are outlined in Table 3. Retention will be defined as alive and receiving ART, as per clinic verified records, within 3 months of the 12-month endpoint. Viral suppression will be defined as <1000 copies/ml. We will also collect data on factors that might impact the primary outcome (as described above).

*Infant outcomes:* We will also abstract data and/or ask the mother information regarding pregnancy and infant outcomes from existing MOH patient records. Data will include information related to the pregnancy and delivery (ie. pregnancy loss, stillbirth, date of birth, gestational age at birth, pre-term birth, small for gestational age, congenital anomalies, birth weight), and data related to the infant, (ie. infant HIV test dates and results, infant ART initiation date, infant retention and survival outcomes, and outcome dates).

**Table 3.** VITAL Start study outcomes and schedule measures

Schedule (Month number)
Informed consent
Aim 1 Retention and Adherence (VL<1000 copies/ml) at 12-month
Retention in care (Data abstraction from electronic medical records)
Viral suppression (VL <1000 copies/ml)123,165
DBS collection for VL at 6 and 12 months
Aim 1b: Behavioral adherence
Self-reported adherence
Pharmacy refill data abstraction
DBS for pharmacokinetic analysis at 12 months

Aim 1c: Knowledge and psychosocial impact
HIV/ART knowledge and attitudes survey
Adherence self-efficacy
Motivation & behavior skills assessment-Life Windows Tool
Self-reported partner disclosure  and World Health Organization intimate partner violence survey and other traumas
Multi-dimensional scale perceived social support (MSPSS)
Self-perceived quality of care
Aim 2: Implementation outcomes
Participant satisfaction surveys
Interviews with participants, partners, health care workers
Study fidelity evaluations
Contamination assessment
Time-motion assessments in line with STAMP checklist
Aim 3: Cost-effectiveness analysis. Data collected throughout study period

**Table 4** outlines the potential moderators of primary health outcomes that may be measured at baseline and follow-up visits.

Table 4. Potential moderators of primary health outcomes	
Collected at Baseline	

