## Data analysis plan:

The intent to treat (ITT) population is defined as all randomized subjects, regardless of when they withdrew from the study. We will exclude the ineligible patients and thus perform modified ITT analysis as the primary analysis to facilitate interpretation if the exclusions do not disrupt the baseline equivalence established by random assignment and bias the results. We also include who completed the intervention, and with follow up data to conduct secondary and exploratory analyses of the secondary efficacy data and explorative outcomes, for example viral load, which is only available at month 6 and 12. There is no planned interim analysis for this study. All hypothesis testing will be

carried out at the 5% (2-sided) significance level unless otherwise specified. Additional ad-hoc analyses may be conducted as deemed appropriate and any changes, including the rationale for use will be documented in the clinical study report. All statistical analysis will be performed using SAS® v9.4, R 4.2.2, Stata 17 or higher for Windows.

Demography and baseline characteristics include age, socioeconomic, pregnancy and HIV variables. etc Descriptive statistics, such as, mean, standard deviation (SD) for continuous variables, and frequency and proportion for categorical variables, will be calculated by treatment group. Baseline differences will be compared using two-tailed independent t-tests (means) and chi-square tests (%) to evaluate the balance of patient characteristics in two groups by the randomization.

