The primary efficacy endpoint is the composite outcome of achievement of retention and viral suppression at Month 12. The primary efficacy endpoint will be analyzed using a binary goal attainment variable (is the achievement of retention and viral suppression [1 yes/0 no]). Participants will be considered retained in care if they are verified by clinic records as active on ART. Retention (1 Yes) will be defined as alive and attending ART clinic, as per clinic verified records, within specified window of the follow up visits. All else without known status or retention information (Due to stopped, LTFU/defaulted, transferred out, missed appointment, and missing) will be defined as Retention (0 No). Amongst those retained the study will then assess viral suppression which will be measured as viral load less than 1,000 copies per milliliter. A sensitivity analysis using detectable vs. undetectable viral load will be performed. Missing viral load information will be treated as not suppressed. There is no missing data on the primary outcome by definition.

The number and proportion of subjects who achieved retention and viral suppression at Month 12 will be summarized by treatment group. The comparison of the proportion of success in the two treatment groups will be conducted using Chi-square tests followed by logistic regression including treatment, center, and other baseline prognostic factors. Important baseline prognostic factors of the main outcome (p-values < 0.2 from univariate analysis) will be entered into the model. The main exposure variable and any factors, such as age, prior history of ART, deemed to be clinically relevant will be forced into the model regardless of the statistical significance. A backwards selection procedure will be performed to select other factors. Variables achieving statistical significance will be retained in the model. Covariates will be checked for collinearity using the variance inflation factor. Where collinearity occurs between two variables, only one of these variables will be included in the final model. An assessment of the model goodness-of-fit will be performed using the Hosmer-Lemeshow test, deviance test, and visual inspection of index plots. The adjusted odds ratio of achieving retention and adherence at Month 12 on VITAL Start versus Control will be reported along with the 95% confidence interval and 2-sided p-value.

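### The month-12 composite carries two significance levels: 0.025 for sizing, for comparisons never named, and a 5% default for analysis

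*Combined protocol and SAP*

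**What the plan says.** **Sizing.** The Sample Size Calculation section introduces its requirement with "For the primary analysis in all subjects, accounting for up to a 15% contamination rate" and concludes that "796 subjects are required (398/398 per arm) at a significance level=0.025 to account for multiple comparisons". It does not identify the comparisons or give the sidedness of the level.

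**Analysis.** The Data analysis plan says that all hypothesis testing is "carried out at the 5% (2-sided) significance level unless otherwise specified". It adds: "There is no planned interim analysis for this study". The comparison of the composite between arms "will be conducted using Chi-square tests followed by logistic regression including treatment, center, and other baseline prognostic factors". No level is attached to the chi-square test. For the regression, the "adjusted odds ratio of achieving retention and adherence at Month 12 on VITAL Start versus Control will be reported along with the 95" per cent confidence interval and a two-sided p-value. No section describes a multiplicity procedure.

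**Primary outcome.** The Data analysis plan states: "The primary efficacy endpoint is the composite outcome of achievement of retention and viral suppression at Month 12". The Sample Size Calculation section agrees, and the secondary outcomes include retention alone at month 12. Outcome Measures gives a list of three: "The main study outcomes are (1) composite of retention and adherence (viral suppression); (1b) behavioral adherence; and (1c) knowledge and psychosocial impact". Specific aim 1, under Objectives and Hypotheses, instead places the primary-outcome label directly after retention in care.

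**The concern.** A trial needs one threshold for its primary endpoint, fixed before anyone sees results by arm. Here the level used to size the primary analysis is half the level that the analysis text uses by default. The reason given for the smaller level refers to comparisons that the reader cannot identify.

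The exception clause in the 5% default could be taken to let the sizing paragraph govern. But the paragraph that defines the primary analysis never takes up 0.025, and its only interval is at 95%. If 0.025 governs, that interval does not match the test. If 5% governs, the sizing paragraph describes an adjustment that the analysis does not make. Text must change in either case.

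At stake is the conclusion for any primary p-value between 0.025 and 0.05. The Aim 1 label adds to the confusion, because a reader may suppose that retention and the composite are two primaries sharing 5%.

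**Working it through.** **Inputs from the Sample Size Calculation section:** 90% power, a 15-point difference, Pearson chi-square, 1:1 allocation, up to 15% contamination, 5% attrition, 398 per arm (446 after a 12% increase), and 800 enrolled, taken as 400 per arm. Only ranges are given for the control rate: retention 50–90% and suppression 50–90%, so the composite lies between 0.50 × 0.50 = 25% and 0.90 × 0.90 = 81%.

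**Assumptions:** control rate 45% (0.50 × 0.90, a corner of that grid); contamination in the control arm only; 0.025 read as two-sided.

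**1. The plan's own figure.** Contamination moves the control rate to 0.45 + 0.15 × 0.15 = 0.4725. Against 0.60 the difference is 0.1275, and the mean rate is 0.53625.

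n = [z(1−α/2)·√(2p̄(1−p̄)) + z(0.90)·√(p1(1−p1) + p2(1−p2))]² / d²

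- α = 0.025: [2.2414 × 0.7052 + 1.2816 × 0.6995]² / 0.1275² = 377.5, so 378. Then 378/0.95 = 397.9, so **398 per arm, 796 in total**, as printed. 398 × 1.12 = 445.8, so 446.
- α = 0.05: [1.9600 × 0.7052 + 1.2816 × 0.6995]² / 0.1275² = 319.4, so 320. Then 320/0.95 = 336.8, so **337 per arm, 674 in total**.

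The printed size is thus consistent with a real halving of 5%, although the inputs needed to confirm this are not all stated.

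**2. Where the two levels disagree.** The smallest significant observed difference with 400 per arm is z·√(2p(1−p)/400):

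| Pooled rate | At 5% | At 0.025 |
|---|---|---|
| 50% | 6.93 points | 7.92 points |
| 25% | 6.00 | 6.86 |
| 81% | 5.44 | 6.22 |

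**3. Example with assumed counts**, control 180/400:

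- Intervention 208/400 (7.0 points): p = 0.048, unadjusted odds ratio 1.32, 95% interval 1.003 to 1.75, 97.5% interval 0.963 to 1.82.
- Intervention 211/400 (7.75 points): p = 0.028, odds ratio 1.36, 95% interval 1.033 to 1.80, 97.5% interval 0.993 to 1.88.

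Both succeed at 5% and fail at 0.025.

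**4. How likely this is.** The probability of an observed difference between 6.93 and 7.92 points, with rates centred on 50%, is Φ((7.92−δ)/se) − Φ((6.93−δ)/se), where se is about 3.5 points:

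| True difference δ | Probability |
|---|---|
| 15 points | 1.1% |
| 12.75 | 3.6% |
| 10 | 8.6% |
| 7.44 (maximum) | 11.2% |

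**5. Power at each level**, 45% control rate, 378 to 400 per arm:

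| Contamination | 0.025 | 5% |
|---|---|---|
| 15%, control arm only | 90–92% | 94–95% |
| None (the pilot figure) | 97–98% | about 99% |

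**6. Interval width.** 2.2414/1.9600 = 1.14, so on the log odds scale a 97.5% interval is about 14% wider than a 95% interval.

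**The case against.** The best defence is that the analysis section is coherent when read alone. It has a 5% two-sided default, a primary paragraph that specifies nothing different, and a 95% interval with a two-sided p-value. On that reading 0.025 is only a sizing assumption, and sizing at a stricter level than the test is conservative. Much of this stands. The two passages do not flatly contradict each other, and the 5% reading is reasonable. It does not close the question, because the sizing paragraph speaks of the primary analysis and gives a multiplicity reason for its level. That can fairly be taken as the exception that the default allows.

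It can also be said that the impact is small. That is right: the 11% maximum needs a true effect near 7.4 points, about half of the 15 points that the plan treats as the least that matters clinically.

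Several stronger readings are tempting, and the documents do not support them:

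- **Inflated type I error.** Two independent co-primaries each tested at 5% would give 1 − 0.95² = 9.75%. But the analysis plan has one primary endpoint and lists month-12 retention as secondary. For a sole primary, 5% two-sided is a valid level.
- **0.025 meant as one-sided.** A size of 398 also arises at 5% two-sided with a 65% control rate and contamination in both arms, so the number alone does not identify alpha. But the stated reason is multiplicity, and the analysis text is two-sided throughout.
- **Nothing could explain 0.025.** There is no interim analysis, and 0.05/3 for three main outcomes is not 0.025. Pairs can still be found, such as retention and adherence in Aim 1, partner and maternal outcomes, or the composite at months 6 and 12. What can be said is that the comparisons are not named.
- **An underpowered trial.** Low power appears only if contamination runs in both directions. The plan describes no such model, and it reports none in the pilot and far less than expected in the trial.

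**Conclusion.** The concern holds as an unreconciled decision threshold. Two levels are on the page for the month-12 composite, and the plan does not say which one decides the result. The disputed zone is an observed difference of about 6.9 to 7.9 points with 400 per arm and rates near 50%, and it sits lower at more extreme rates. The chance of landing in it is about 1% if the design effect of 15 points is true and about 11% at worst. These figures read 0.025 as two-sided and ignore covariate adjustment.

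The Aim 1 label is a separate slip. The Sample Size Calculation section, the primary endpoint paragraph and the list of secondary outcomes all settle it in favour of the composite. None of the figures depends on it.

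**What to change.** In Specific aim 1, name the month-12 composite as the sole primary outcome. State one two-sided alpha for it, with a matching confidence interval, in the Sample Size Calculation section and the Data analysis plan, before the group code is broken. There are two coherent choices:

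- **Keep 0.025:** report a 97.5% interval and name the comparisons that share alpha. The cost is an interval about 14% wider. Power is about 90–92% with one-way contamination, or 97–98% with none.
- **Use 5%:** keep the 95% interval, delete the reference to multiple comparisons, and restate the sizing. That means about 337 per arm for 90% power, or about 94–95% power with 378 to 400 per arm, under 15% one-way contamination.

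These figures assume a 45% control rate.

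Enrolment is already reported as complete, and the documents do not show whether the code is still sealed. If it has been broken, judge the primary result at the stricter 0.025 and report the 5% reading as such, so that the level is not chosen after seeing the data. The change is to wording only and needs no new data.

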## Outcome Measures

The main study outcomes are (1) composite of retention and adherence (viral suppression); (1b) behavioral adherence; and (1c) knowledge and psychosocial impact. Additional outcomes and schedule of measures are outlined in Table 3. Retention will be defined as alive and receiving ART, as per clinic verified records, within 3 months of the 12-month endpoint. Viral suppression will be defined as <1000 copies/ml. We will also collect data on factors that might impact the primary outcome (as described above).

*Infant outcomes:* We will also abstract data and/or ask the mother information regarding pregnancy and infant outcomes from existing MOH patient records. Data will include information related to the pregnancy and delivery (ie. pregnancy loss, stillbirth, date of birth, gestational age at birth, pre-term birth, small for gestational age, congenital anomalies, birth weight), and data related to the infant, (ie. infant HIV test dates and results, infant ART initiation date, infant retention and survival outcomes, and outcome dates).

**Table 3.** VITAL Start study outcomes and schedule measures

Schedule (Month number)
Informed consent
Aim 1 Retention and Adherence (VL<1000 copies/ml) at 12-month
Retention in care (Data abstraction from electronic medical records)
Viral suppression (VL <1000 copies/ml)123,165
DBS collection for VL at 6 and 12 months
Aim 1b: Behavioral adherence
Self-reported adherence
Pharmacy refill data abstraction
DBS for pharmacokinetic analysis at 12 months

Aim 1c: Knowledge and psychosocial impact
HIV/ART knowledge and attitudes survey
Adherence self-efficacy
Motivation & behavior skills assessment-Life Windows Tool
Self-reported partner disclosure  and World Health Organization intimate partner violence survey and other traumas
Multi-dimensional scale perceived social support (MSPSS)
Self-perceived quality of care
Aim 2: Implementation outcomes
Participant satisfaction surveys
Interviews with participants, partners, health care workers
Study fidelity evaluations
Contamination assessment
Time-motion assessments in line with STAMP checklist
Aim 3: Cost-effectiveness analysis. Data collected throughout study period

**Table 4** outlines the potential moderators of primary health outcomes that may be measured at baseline and follow-up visits.

Table 4. Potential moderators of primary health outcomes	
Collected at Baseline	
Maternal socio-demographics:	age, educational level, literacy, hunger in past month, mom employment status, economic status, self-reported comfort with technology and literacy, pregnancy information [trimester of pregnancy, primiparous, number of children],
Maternal sexual history:	duration with current sexual partner, number of sex partners in past year 
HTC history:	never tested, previously negative, previously positive, previous history of couples HIV testing and counseling
Partner related:	partner age, education status, employment status, perception of partner HTC history  (no test/does not know, negative, positive, indeterminate), perception of partners sexual activity (number of sex partners in past year, belief partner has had other partners in the past year),  experience with intimate partner violence (IPV) or perceived threat of IPV (yelled at or threatened by partner, physically hurt by partner, fear of partner being angry with disclosure, fear of being left by partner if disclosed, fear of being hurt, fear of partner telling others) 
Maternal health behaviors and depression:	adherence self-efficacy, family planning related, alcohol/drug use, perceived social support  depression and anxiety  ART side effects

## Data collection and management

All questionnaires used for data collection purposes will be translated into Chichewa (the local language), back-translated, and pilot tested prior to use, and will be administered by study staff. Attached here is the draft questionnaire.

## Data analysis plan:

The intent to treat (ITT) population is defined as all randomized subjects, regardless of when they withdrew from the study. We will exclude the ineligible patients and thus perform modified ITT analysis as the primary analysis to facilitate interpretation if the exclusions do not disrupt the baseline equivalence established by random assignment and bias the results. We also include who completed the intervention, and with follow up data to conduct secondary and exploratory analyses of the secondary efficacy data and explorative outcomes, for example viral load, which is only available at month 6 and 12. There is no planned interim analysis for this study. All hypothesis testing will be

carried out at the 5% (2-sided) significance level unless otherwise specified. Additional ad-hoc analyses may be conducted as deemed appropriate and any changes, including the rationale for use will be documented in the clinical study report. All statistical analysis will be performed using SAS® v9.4, R 4.2.2, Stata 17 or higher for Windows.

Demography and baseline characteristics include age, socioeconomic, pregnancy and HIV variables. etc Descriptive statistics, such as, mean, standard deviation (SD) for continuous variables, and frequency and proportion for categorical variables, will be calculated by treatment group. Baseline differences will be compared using two-tailed independent t-tests (means) and chi-square tests (%) to evaluate the balance of patient characteristics in two groups by the randomization.

The primary efficacy endpoint is the composite outcome of achievement of retention and viral suppression at Month 12. The primary efficacy endpoint will be analyzed using a binary goal attainment variable (is the achievement of retention and viral suppression [1 yes/0 no]). Participants will be considered retained in care if they are verified by clinic records as active on ART. Retention (1 Yes) will be defined as alive and attending ART clinic, as per clinic verified records, within specified window of the follow up visits. All else without known status or retention information (Due to stopped, LTFU/defaulted, transferred out, missed appointment, and missing) will be defined as Retention (0 No). Amongst those retained the study will then assess viral suppression which will be measured as viral load less than 1,000 copies per milliliter. A sensitivity analysis using detectable vs. undetectable viral load will be performed. Missing viral load information will be treated as not suppressed. There is no missing data on the primary outcome by definition.

The number and proportion of subjects who achieved retention and viral suppression at Month 12 will be summarized by treatment group. The comparison of the proportion of success in the two treatment groups will be conducted using Chi-square tests followed by logistic regression including treatment, center, and other baseline prognostic factors. Important baseline prognostic factors of the main outcome (p-values < 0.2 from univariate analysis) will be entered into the model. The main exposure variable and any factors, such as age, prior history of ART, deemed to be clinically relevant will be forced into the model regardless of the statistical significance. A backwards selection procedure will be performed to select other factors. Variables achieving statistical significance will be retained in the model. Covariates will be checked for collinearity using the variance inflation factor. Where collinearity occurs between two variables, only one of these variables will be included in the final model. An assessment of the model goodness-of-fit will be performed using the Hosmer-Lemeshow test, deviance test, and visual inspection of index plots. The adjusted odds ratio of achieving retention and adherence at Month 12 on VITAL Start versus Control will be reported along with the 95% confidence interval and 2-sided p-value.

Secondary efficacy outcomes include achievement of retention and viral load suppression at month 6, retention at month 12, viral suppression at month 12, TFV-DP and 3TC adherence status at month 12 (for selected subcohort), and self-reported adherence status at month 12. The statistical method detailed above will be applied.

Other explorative measures include knowledge inventory, patient-Provider relationship, pregnancy intention, satisfaction with the counselling, adherence-self efficacy, partner disclosure, motivation and behavior skills, perceived social support, self-Reporting Questionnaire (SRQ)- Mental health assessment (depression and anxiety), adverse Childhood Events – International Questionnaire (ACE-IQ), cigarette use, alcohol use disorders identification test (AUDIT), drug use disorders Identification Test (DUDIT), family planning intentions, side effects, intimate partner violence (IPV), contamination measures, infant outcomes and COVID-19 impact. Descriptive statistics will be calculated for all measures and displayed by treatment group and visit as appropriate. For continuous outcomes, such as ART knowledge measures, adherence self-efficacy score, motivation and behavioral skills, perceived social support score and self-perceived patient-provider quality of HIV care score, two-

sample t-tests will be used to compare 12-month outcomes and linear mixed models will be used to examine differences in trajectories over time between the intervention and control groups. For categorical outcomes, the number and proportion of the categories at Month 12 will be compared using Chi-square tests. Generalized Estimating Equation (GEE) method for repeatedly measured categorical outcomes will be applied to compare the outcome across time between two groups while accounting for the correlation among repeated measures from the same subject.

---

**Specific aim 2: To critically examine the delivery of VITAL start** via in-depth interviews and surveys administered to patients, partners, and health workers. Adoption and satisfaction with the program will be measured. Qualitative interviews will be utilized to obtain feedback on motivational qualities of the program and benefits and challenges of delivery.

---

**Participant eligibility and recruitment:** All participants enrolled in the study, their partners, as well as healthcare providers working at the study sites will be eligible for participation. Purposeful sampling will be used to maximize variability in the sample, ensuring that a broad range of views, demographic factors (for example, income age, marital status), social factors, study sites, and outcomes (disclosed to partners/LTFU) are represented.

To assess overall satisfaction with the intervention both HCWs and study participants will be asked to complete satisfaction surveys. In addition, an objective assessment regarding the impact of the intervention on HCW efficiency and time spent on counseling will be conducted with use of time-motion assessments in line with the STAMP checklist (Suggested Time and Motion Procedures).

**Interviews:** To further explore implementation issues that may be unique for women, partners, and HCWs, we will conduct in-depth interviews. We plan to interview approximately up to ~100 women (50 intervention/50 control group), 40 partners (20 intervention/20 control group), and 40 HCWs with the final sample size determined by data saturation. Women will be invited by the research assistant to participate in qualitative interviews during follow up visits. Some women may be asked for repeated interviews (for example at baseline, 1 month follow up as well as 6 month follow up). A sample of partners of women participating in the study will be recruited for participation. Study staff will invite healthcare workers.

**Data collection:** *Interview guide:* The study team and interviewer(s) will co-develop the guides. All participants will be asked about their views on the feasibility and acceptability of the video intervention, as well as its strengths, suggestions for improvement, motivational aspects, and the challenges and benefits they experienced. We will assess if the video accurately communicated intended educational messages, and if unintentional messages were portrayed. We will ask about experiences with partner disclosure and ART adherence. We will also use qualitative research to help explain/describe quantitative findings. HCWs will be asked about the challenges and benefits to implementing VITAL start and its potential impact on the health facility and patients. They will also be asked about the integration of videos into others aspects of health care delivery. To ensure proper translation, the patient guide will be translated into Chichewa, back-translated into English, pre-tested and revised to ensure comprehension. *Interviewers:* experienced qualitative interviewers will conduct the interviews. *Interview procedure for all participants:* Interviews will be conducted at the location of the participants choosing or via phone if that is the participant's preference. Informed consent will be obtained for enrollment in this nested sub-study from all participants. Interviews will be conducted in Chichewa, unless the participant is fluent and wishes the interview to be conducted in English. Interviews are expected to take 30 to 60 minutes and will be digitally recorded and transcribed verbatim. Interviewers will also take notes during the interviews.

**Data analysis:** *Transcription:* Recorded interviews will be transcribed verbatim and translated into English and occur concurrently with data collection. *Coding:* Transcript text will be read and re-read carefully to: (1) become familiar with each individual situation; (2) identify text that may be unclear due

to differences in the cultural context; (3) point out areas in which interviewing techniques could be improved; and (4) identify recurrent themes. We will use standard qualitative content analysis approaches for thematic analysis of the transcripts. Study staff experienced in qualitative data analysis will code the scripts and establish a coding scheme. The developed coding scheme will be refined to enable one research team member to independently code the remaining transcripts, with revisions made as necessary to reflect new and evolving themes. Thematic analysis will occur concurrently with data collection to allow further exploration and clarification of emergent ideas, and data collection will continue until data saturation is reached. Transcribed interviews and digital files will be stored on a password-protected computer, and when not in use will be stored under lock and key. All data will be anonymized for publication. Only researchers affiliated with the study will have access to participant data.

---

**Specific aim 3: To assess the cost-effectiveness of the VITAL start intervention.** Cost-effectiveness will be assessed using incremental cost-effectiveness ratios, with health effects expressed in term of viral load suppression and costs of resources used for the intervention.

---

**Costing:** The MOH will be the main implementer of the VITAL start intervention as well as standard of care pre-ART counseling. Therefore, we will assess costs from the provider (MOH) perspective. We will use both micro and macro based approaches as appropriate to identify and quantify intervention resources. Retrospectively, we will extract information on resources expended for video design and production from inventory and other BCM-CFM Tingathe program documents. Unit prices will be obtained from accounts records or from local retailers.

Prospectively, we will collect information regarding costs of administering both the VITAL start and the SOC pre-ART counseling. To measure staff time devoted to pre- ART counseling, we will perform time-motion assessments in line with the STAMP (Suggested Time and Motion Procedures). We will sample sufficiently to account for potential sources of heterogeneity such as study clinic and provider. We will randomly sample provider sessions from each arm of the study and each participating study clinic during every month of participant enrolment. A minimum of 4 assessments will be conducted per clinic every month. Therefore, we anticipate collecting data on over 200 pre-ART counseling sessions. Repeat sampling of providers is expected and will be recorded. The value of staff time will then be estimated as the product of their gross salary and share of time allocated to intervention/pre ART counseling.

**Cost effectiveness analysis:** We will calculate incremental cost-effectiveness ratio (ICER), for the primary outcome of economic interest: proportion of women virally suppressed at 6 months follow up. The ICER is the difference in costs between two interventions divided by the difference in their effects, and can be interpreted as the incremental price of a unit health effect from the intervention under study, as compared to the alternative.

We will conduct one way and multi-way sensitivity analysis to model cost-effectiveness under various conditions, such as lower pricing of video production, mode of delivery, tablets, and alternate health care workers cadres to deliver the intervention. Finally, we will conduct probabilistic sensitivity analysis using bootstrapping methods to ascertain robustness of our results to extreme assumptions/scenarios. Based on emerging literature, we will define VITAL start as cost-effective if its ICER is < 50% of Malawi GDP ( $0.5 \times \$250 = \$125/\text{YLS}$ ), compared to standard pre-ART counseling. We will also consider alternative thresholds of 100% and 300% of GDP.

